This project seeks to elucidate the mechanisms by which antidepressant medications have limited efficacy in Late Life Depression (LLD)¹ in order to develop new treatment interventions for this prevalent and disabling illness.²⁻³ We hypothesize that the presence of executive dysfunction (ED), which is common in depressed adults over 60,⁴ impairs the ability to form appropriate expectancies of improvement with antidepressant treatment. Greater expectancy has been shown to improve antidepressant treatment outcome and is hypothesized to be a primary mechanism of placebo effects.⁵⁻⁷ Moreover, white matter hyperintensities (WMH) on magnetic resonance imaging (MRI) are more prevalent in patients with LLD compared to age-matched healthy controls.⁸ It has been argued that WMH contribute to the pathogenesis of LLD with ED and decrease the efficacy of antidepressant medications by disrupting connections between prefrontal cortical (PFC) and subcortical structures.⁹⁻¹⁰ Vascular lesions to white matter tracts may also compromise the pathway by which expectancy-based placebo effects influence depressive symptoms. Expectancies reflect activation in PFC areas that may improve depressive symptoms by modulating the activity of subcortical regions subserving negative affective systems (i.e., amygdala)¹¹⁻¹² as well as those important in reward and hedonic capacity (nucleus accumbens and ventral striatum).¹³⁻¹⁴ Thus, LLD patients with ED and WMH may sustain a “double-hit” to their ability to experience placebo effects in antidepressant treatments: ED diminishes the ability to generate appropriate treatment expectancies, while WMH disrupt the physiologic pathways by which expectancies lead to improvement in depressive symptoms.

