**Data analysis plan. Overview:**

The proposed trial will enroll 130 patients aged 60-90 years and randomize them to open label treatment with escitalopram

(n=60) vs. a double-blind

escitalopram-placebo trial (n=70, with n=60 to escitalopram and n=10 to placebo). Hence, participants in the double-blind condition will not know whether they are receiving drug or placebo. Patients will vary in their baseline severity of ED and WMH burden, which will be measured using the Stroop Color-Word Test and the Fazekas modified Coffey Rating Scale of anatomical MRI images, respectively. Specific Aim 1 focuses on determining whether differences in expectancy and depression outcomes found over time between the two randomized conditions are *moderated* by baseline ED and WMH measures (i.e., whether more severe ED and/or WMH are associated with smaller differences between the open and placebo-controlled conditions). Specific Aim 2 investigates whether poor antidepressant outcome (regardless of randomized condition) is associated with more severe baseline ED and WMH burden, and whether this association is *mediated* by decreased patient expectancy. In the Exploratory Aim, we are interested in using DTI to explore with greater anatomical precision the white matter damage associated with smaller differences in patient expectancy and antidepressant outcome between the open and placebo-controlled conditions.

Before the specific statistical techniques are applied, we will examine all variables at all time points for illegitimate values, outliers, and inconsistencies. The distribution of demographic variables, rater-administered and self-report measures will be examined and described in terms of means, standard deviations, minima, and maxima for continuous variables, and proportions for categorical variables. Missing data: We will make every effort to obtain all data. The longitudinal mixed modeling described below imputes unobserved time points using observed data from the individual combined with the overall trend. Inferences are valid if missing data are missing at random (MAR). MAR assumptions cannot be verified. A 2010 national expert panel recommended sensitivity analyses for the impact of missing data via pattern mixture models, which we will conduct (e.g., by investigating robustness of results to perturbations of assumed values for missing data within clinically plausible ranges).

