
Analyses for Specific Aim 2: Hypothesis: ED and WMH will be associated with decreased change in depressive symptoms, and this association will be mediated by a decreased contribution of expectancy to antidepressant outcome. The first part of this hypothesis will be tested using a longitudinal mixed effect for HRSD scores as in Model 1 but only including predictors that do not involve randomized condition, i.e.  $\beta_0, \beta_1, \beta_2, \beta_6, \beta_9$ . The tests of interest are the main effect for ED/WMH and its interaction with time (i.e.  $\beta_4$  and  $\beta_6$ ). After having established an overall effect of ED and/or WMH on depression outcome (i.e., HRSD), we will test

$$\text{MODEL 1: } Y_{ij} = \beta_0 + \beta_1 y_{i0} + \beta_2 g(t_j) + \beta_3 I_i^{TRT} + \beta_4 ED/WMH_i + \beta_5 g(t_j) * I_i^{TRT} + \beta_6 g(t_j) * ED/WMH_i + \beta_7 I_i^{TRT} * ED/WMH_i + \beta_8 g(t_j) * I_i^{TRT} * ED/WMH_i + \beta_9 X_i + b_i + \epsilon_{ij}$$

[figure not shown]

Figure 5. Mediation of the relationship between ED/WMH and antidepressant outcome by a loss of expectancy effects.

$\beta_4$ ,

expectancy as a mediator of the relationships (see Figure 5). To be a mediator we must establish that expectancy is affected by ED/WMH and that it influences antidepressant outcome controlling for ED/WMH. In order to ensure time order of the mediator (expectancy) occurring prior to the depression outcome (HRSD), we will use early change in expectancy (i.e., from baseline to week 1) as the primary measure for the mediator. A model with week 1 expectancy as the outcome and ED/WMH as the primary predictor, controlling for baseline covariates, will be used to estimate path a in Figure 5. To estimate path b in Figure 5, the same longitudinal mixed effect model described above with the addition of week 1 expectancy as a predictor will be used. The mediation effect is estimated by taking the product of the estimates for a and b and using the bootstrap method to obtain standard errors, confidence intervals, and the test for statistical significance. Recent developments in mediation analysis suggest the need for sensitivity analyses to explore potential impact of unmeasured confounders. We will perform these sensitivity analyses with the new mediation R package that provides a range of plausible results that may have been obtained under different assumptions about unmeasured confounders.

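### Aim 2's product of paths a and b tests lowered expectancy but not a weakened link from expectancy to symptoms, which Hypothesis 2 also covers

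*SAP*

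**What the plan says.** Hypothesis 2, in the protocol (Specific Aims and Hypotheses) and the SAP (Analyses for Specific Aim 2), is that the association of ED and WMH with poorer outcome is "mediated by a decreased contribution of expectancy to antidepressant outcome". The Figure 5 caption reads "Mediation of the relationship between ED/WMH and antidepressant outcome by a loss of expectancy effects". The protocol's model has two parts: ED impairs the forming of expectancies, while "WMH disrupt the physiologic pathways by which expectancies lead to improvement in depressive symptoms". The SAP Overview states Aim 2 more narrowly, as mediation "by decreased patient expectancy".

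The planned analysis runs as follows:

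- **Criterion:** "To be a mediator we must establish that expectancy is affected by ED/WMH", and that expectancy influences outcome after controlling for ED/WMH.
- **Path a:** week-1 expectancy regressed on ED/WMH and baseline covariates.
- **Path b:** the Aim 2 HRSD model with week-1 expectancy added. The nearest preceding model is the one "only including predictors that do not involve randomized condition".
- **Test:** "The mediation effect is estimated by taking the product of the estimates for a and b", with bootstrap inference.

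No expectancy × ED/WMH term is described. The only mediation sensitivity analysis concerns unmeasured confounding.

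**The concern.** The two parts of the protocol's model act at different places. Lowered expectancy is path a. A disrupted route from expectancy to symptoms is a change in the slope of path b with WMH. A single b, common to all patients, cannot show that change, so the product addresses only the first part.

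At stake is how a null product is read. If WMH work partly or wholly by weakening the link, that part appears as a direct WMH effect. It could then be reported as evidence against expectancy as the mechanism, when loss of the expectancy effect is what the hypothesis proposes.

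**Working it through.** The documents give no effect size or power for Aim 2, so there is no stated figure to reproduce.

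**Algebra (no effect sizes needed).** Let W be standardised ED/WMH, M expectancy gain with mean mu, and Y symptom improvement:

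- M = mu + aW + error
- Y = c'W + (b + hW)M + error, where h is the change in slope per SD of W

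For symmetric W, or a = 0, the linear effect of W on Y is c' + ab + h·mu. The planned product targets ab. Without the interaction, h·mu goes into the W coefficient, which is reported as the direct effect. If a = 0, ab = 0 for every h.

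Example with both mechanisms (assumed a = -0.3, b = 0.4, h = -0.3, mu = 1, c' = 0): ab = -0.12, h·mu = -0.30, total -0.42. Simulated means at n=120 were -0.121 for the product and -0.422 for the total. The product was significant in 84% of trials but recovered 0.121/0.422 = 29% of the effect.

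**Link loss only (a = 0).** Inputs from the documents: n = 130 - 10 = 120 for HRSD (SAP, Aim 1); 90 completers required (Protocol, Description of Subject Population); two-sided 0.05 (stated under Aim 1, assumed to apply to Aim 2). Assumed: DWMH scores 0/1/2/3 in 15/45/25/15% of patients; mu = 1 SD; condition raises expectancy 0.5 SD; slope 0.3 - kW; residual SD 1; one endpoint per patient in place of the mixed model. There were 1,500 trials per setting and 400 bootstrap resamples.

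| n=120 | k=0.1 | k=0.15 | k=0.2 |
|---|---|---|---|
| Slope at DWMH 0 / 3 | 0.45 / 0.13 | 0.53 / 0.04 | 0.61 / -0.05 |
| Total WMH effect significant | 18% | 34% | 53% |
| Planned product significant | 5% | 6% | 5% |
| Expectancy × WMH significant | 18% | 36% | 58% |
| Condition × WMH on outcome (Aim 1 analogue) | 6% | 6% | 9% |
| Direct effect, no mediation, given significant total | 84% | 85% | 92% |

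Hand check of the interaction row: its standard error is about 1/√120 = 0.091, so k/SE = 1.1, 1.6 and 2.2, which gives power near 20%, 37% and 59%.

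Share of all trials reporting a direct effect without mediation: 0.18 × 0.84 = 15%, 0.34 × 0.85 = 29%, 0.53 × 0.92 = 49%. A repeat run gave 14%, 26% and 48%, and 33% at n=90 with k = 0.2. At n=90 the product is significant in 4-5% of trials and the interaction in 17%, 28% and 47%.

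**Dependence on the assumptions (n=120).**

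- Mean gain 0.5 SD: the total effect is significant in only 8% (k = 0.1) and 19% (k = 0.2); the product stays at 5%.
- WMH also lower expectancy (a = -0.3): the product is significant in 77%, and a direct effect without mediation is reported in about 8%. At a = -0.2 the product is significant in about 50%.
- Less noise (residual variance 0.65): interaction 28.5%, 51%, 74%; product about 6%.

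**Why Aim 1 has little power here.** Link loss reaches the condition contrast only through the expectancy gap. The condition × WMH effect is k × 0.5 = 0.05 to 0.10, against a standard error of about 2 × 1.06/√120 = 0.19. With a 1 SD expectancy gap, rejection is 8.5% at k = 0.1 and 17.6% at k = 0.2.

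**Randomised condition left out of path b.** Suppose condition moves expectancy by dm and HRSD by dy through other routes, and the true b is 0. The fitted b is then about 0.25·dm·dy/(1 + 0.25·dm²): 0.0375/1.0625 = 0.035 for dm 0.5, dy 0.3, and 0.10/1.16 = 0.086 for dm 0.8, dy 0.5. With a = -0.4, false mediation occurs in 6.5-19% of trials without condition and 5-7% with it; a repeat run gave 10-18% and 6-8%.

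**The case against.** **The product is the right test of the aim as the Overview words it.** A factor that changes only the slope is a moderator, and the SAP puts moderation in Aim 1. This stands in part: the product is valid for lowered expectancy and should stay. But Hypothesis 2 is worded as decreased contribution, and the protocol's WMH mechanism is explicitly about the link.

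**Aim 1 already covers it.** The protocol measures the expectancy contribution by the open versus placebo-controlled difference, and Model 1 is fitted to both expectancy and HRSD. A preserved expectancy gap with a shrunken HRSD gap would point to link loss, on a randomised contrast. That is relevant, but β8 on HRSD alone cannot separate the two mechanisms, and its power for link loss was low in every setting tried.

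**WMH with no effect on expectancy is an edge case.** The protocol's background has vascular lesions causing ED, and ED lowering expectancy. Hypothesis 1 expects both ED and WMH to shrink expectancy differences. This stands and limits the harm, as the a = -0.3 result shows.

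**Stronger readings.** A reader might infer that Aim 2 would usually report a direct WMH effect with no mediation. The documents do not support that. It needs a near zero and a sizeable mean expectancy gain, and neither is given. The protocol's preliminary study reports little expectancy change in patients aged 60 or over, possibly meaning between conditions. Even under the assumptions used, the share of all trials is below half. A reader might also take "After having established an overall effect of ED and/or WMH on depression outcome" as a gate on reporting the indirect effect; the text gives an order and does not say so.

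**Conclusion.** The concern holds in limited form. That the product omits link loss is structural and needs no assumed numbers; it leaves the WMH half of the protocol's model untested within Aim 2. The size of the harm does depend on assumptions. With link loss only and a 1 SD mean gain, the product rejects at about 5%, and a significant total effect is mostly read as non-mediation, in roughly 14-48% of all trials at n=120. The share is smaller with a lower mean gain, and uncommon when WMH also lower expectancy by 0.3 SD. The condition covariate matters only if condition affects HRSD outside week-1 expectancy.

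The simulations use one endpoint in place of the mixed model. The Figure 5 drawing and SAP sections 3.3.B.5-6 were not available; the Aim 2 text describes no interaction. This is an inexpensive improvement worth making. It is not a reason to discard the planned analysis.

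**What to change.** - Keep the planned product, labelled as the test of lowered expectancy.
- Add expectancy × ED/WMH to path b as a secondary analysis, with date and reason, because the protocol's continuation report says interventions are complete. Report the interaction and the expectancy slope at low and high ED/WMH (DWMH score levels; the planned tertiles for Stroop) with bootstrap intervals. An indirect effect conditional on ED/WMH is not a substitute: it is a times the slope, so it is also zero when a = 0.
- Include randomised condition as a covariate in paths a and b. It is designed to move expectancy and may affect HRSD by other routes.
- Use one definition of the mediator in the SAP Overview and the Aim 2 analysis.
- State that power for the interaction is modest, so a null does not show an intact link, and that a null product does not rule out link loss.

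**Cost:** SAP wording and two model terms on data already held. Intervals widen slightly, there are a few more estimates without multiplicity control, and the additions are post hoc. WMH analyses may have fewer than 120 patients, since the protocol lets patients unsuitable for MRI join the clinical trial unscanned.

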2. Should a subject ask about the specific chances of being assigned to placebo or escitalopram [or duloxetine] in the Placebo Controlled Group, we will respond: “For the purpose of maintaining the study integrity, certain details of the study must be temporarily withheld from you. These details include your exact chances of receiving placebo or escitalopram [or duloxetine]. However, we can tell you that your chances of receiving placebo in this study are no greater than 50%. Also, following the conclusion of your participation in the study, we will provide you with the complete details of the study design if you so wish.” This approach allows the patient sufficient information to judge whether they wish to continue participating in the study while ensuring that the data produced are informative. Of course, subjects may choose to withdraw informed consent and not participate in the study if they are not comfortable with this level of specificity.

3. Patients will return to the LLDRC for weekly visits, at which they will receive clinical management (MD) and complete assessment measures conducted by raters blinded to condition assignment. Weekly measures will include HRSD, Hamilton Anxiety Scale (HARS), Clinical Global Impressions (CGI)—Improvement, Credibility and Expectancy Scale (CES), and Quick Inventory for Depressive Symptomatology (QIDS) (MD, RN, or MSW).

4. If a patient discontinues medication due to tolerability problems, ineffectiveness, patient preference, or other reasons, the patient will be dropped out of the study and enter the 3 month long open treatment phase. Appropriate medication options will be discussed with the patient based on their symptoms and history. If the patient wishes, they will be provided referrals for psychotherapy or treatment options outside of our research clinic. No further research measures will be conducted once a patient enters the open treatment phase.

5. Patients in all treatment cells will be discontinued from the acute treatment phase if there is there is a rating of 6 (much worse) or 7 (very much worse) on the CGI—I for 2 consecutive weeks. Patients receiving medication may continue receiving the same medication if clinically indicated after being dropped from the study. No further research measures will be performed on patient dropped from the study.

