Analyses for Specific Aim 1: Hypothesis: Greater ED and WMH will be associated with smaller differences in patient expectancy and antidepressant outcome between the open and placebo-controlled conditions. All tests will be two-sided:  $\alpha=0.05$ , intent-to-treat, with data included for all patients with  $\geq 1$  post-baseline assessment. The primary outcome measure of expectancy (items 2 and 4 of the CES) and antidepressant outcome (24-item HRSD) will be collected at baseline and at weeks 1 through 8. Analysis for expectancy will include all randomized individuals (n=130), analysis for HRSD will drop the n=10 individuals who receive placebo to strictly compare the antidepressant drug outcome of open label vs. double-blind. The hypothesis is addressed by testing the 3-way interaction ( $\beta_8$  in Model 1 below) between baseline ED/WMH, time, and treatment condition. 'ED/WMH' denotes our intention to analyze the effects of ED and WMH individually as well as in combination. The longitudinal mixed effect model (Model 1) will be used where  $Y_{ij}$  is the expectancy or HRSD score for subject  $i$  at  $t_j$  week,  $t_j=1,2,\dots,8$ ,  $y_{i0}$  is expectancy or HRSD at baseline,  $I_i^{TRT}$  is the indicator variable for randomized condition (open label vs. double-blind),  $ED/WMH_i$  is the baseline measure of ED/WMH (see section 3.3.B.6),  $X_i$  includes the randomization stratification variable (i.e., age) and any baseline covariates exhibiting imbalance after randomization,  $b_i$  is a random intercept to account for repeated measures across time within patient, and  $g(t_i)$  is a general function of time to allow for non-linear time trends. We will determine the best way to model  $g(t_i)$  by comparing BIC fit criteria across models including linear, cubic splines, or categorical (i.e., dummy variable) time effects. Model 1 will be fit using PROC GLIMIX in SAS. A significant interaction of  $g(t_i) * I_i^{TRT} * ED/WMH_i$  (corresponding to rejecting the null hypothesis that  $\beta_8 = 0$ ) indicates that the effect of randomized condition on the outcome over time is different by baseline ED/WMH. Because this interaction effect is a function of continuous time and ED/WMH, interpretation will be facilitated by forming contrasts at different fixed values of time (e.g., early vs. late, week 1 vs. week 8) and ED/WMH severity (low vs. moderate vs. high defined by tertiles of baseline ED/WMH distributions). Model 1 will also be used to analyze secondary measures of expectancy (QIDS-SR Expectancy Version) and to test moderator effects of secondary measures of ED and WMH (see sections 3.3.B.5-6.)

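### Aim 2, path b: the week-1 HRSD row is concurrent with the expectancy mediator, and measured improvement by week 1 is left out, so a significant indirect effect may not show that expectancy drove outcome

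*SAP*

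**What the plan says.** The SAP, Analyses for Specific Aim 2, sets two conditions: "To be a mediator we must establish that expectancy is affected by ED/WMH and that it influences antidepressant outcome controlling for ED/WMH". The mediator is the change in expectancy over the first week, chosen "In order to ensure time order of the mediator (expectancy) occurring prior to the depression outcome (HRSD"). Path a regresses week-1 expectancy on ED/WMH and baseline covariates. For path b, "the same longitudinal mixed effect model described above with the addition of week 1 expectancy as a predictor will be used". The indirect effect is the product a×b with a bootstrap test.

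The model that path b reuses comes from Analyses for Specific Aim 1:
- Expectancy and HRSD "will be collected at baseline and at weeks 1 through 8", and the outcome index runs over weeks 1 to 8.
- The only outcome history is y_i0, which "is expectancy or HRSD at baseline".
- The other covariates are the stratification variable (age) and baseline variables found to be imbalanced. Nothing measured after baseline enters.

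The Protocol (Study Procedures, Clinical study, item 3) lists HRSD and the expectancy scale (CES) together among the weekly measures. The SAP also plans "sensitivity analyses to explore potential impact of unmeasured confounders".

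**The concern.** Two things do not fit together.

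First, the mediator is fixed at week 1 to put it before the outcome, yet week 1 is one of the eight outcome rows. The stated time order fails for that row. Weeks 2 to 8 do follow the mediator.

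Second, expectancy at week 1 is not randomised. A patient who already feels better at week 1 may report higher expectancy and is also likely to score lower later. Early improvement is then a common cause of mediator and outcome. It is measured, and path b leaves it out.

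There is also a small gap in wording: the mediator is called a change, but path b names only the week-1 value and no baseline expectancy.

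Aim 2 is the study's mechanistic claim. The Protocol's Specific Aims hypothesise that ED itself "impairs the ability to form appropriate expectancies of improvement with antidepressant treatment". If so, path a is real, and whether a×b is significant depends almost wholly on path b. A positive result could then mean that early improvement raised expectancy, not that expectancy drove improvement.

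**Working it through.** The SAP text available gives no power, effect size or correlation for Aim 2, so there is no planned figure to reproduce. Figure 5 and one section of the SAP were not available to this check.

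**1. Does the bias exist in principle?** Work in residual HRSD SD units, given baseline HRSD and ED/WMH. Let HRSD at week j be a patient state plus weekly error, with state variance ICC and total variance 1. Assume no expectancy effect. With complete data and a random intercept, the coefficient of a time-constant predictor equals OLS on patient means. A mixed-model fit confirmed this: −0.178, SE 0.058 both ways. Take n = 130 − 10 = 120; Aim 1 drops placebo patients from HRSD analyses, and this is assumed for Aim 2.

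If expectancy tracks the observed week-1 score with correlation −r:
- Planned path b tends to −r × [ICC + (1 − ICC)/8]. With the assumed ICC 0.6 and r = 0.2: −0.2 × (0.6 + 0.4/8) = −0.13 (simulated −0.128).
- SE ≈ √[(0.65 − 0.13²)/120] = 0.073, so z ≈ 1.79 and rejection ≈ Φ(1.79 − 1.96) = 43% (simulated 41%).
- Starting at week 2: −0.2 × 0.6 = −0.12 (simulated −0.119; 35% rejection).
- Also adjusting for week-1 HRSD: 0 (simulated 0; 5%).

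If expectancy instead follows the true state, with r now the correlation with that state:
- Unadjusted: −r√ICC = −0.2 × 0.775 = −0.155 (simulated −0.154; 55%).
- Adjusted: −r√ICC(1 − ICC)/(1 − r²ICC) = −0.062/0.976 = −0.063 (simulated −0.063; 23%). Adjustment reduces the bias but does not remove it.

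**2. How large might it be?** All inputs here are assumptions: n = 120; between-patient and residual SDs of 5 and 4 HRSD points; ED effect of 2 points per SD, growing linearly to week 8; ED/WMH directly lowering week-1 expectancy by 0.35 SD per SD; no true expectancy effect. Path a is then nearly always significant (0.35 × √120 = 3.83 against 1.96, taking unit residual SD), so a×b follows path b. False-positive rates:

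| r, week-1 expectancy with week-1 HRSD | Patient effect constant over weeks | State drifts (week-to-week correlation 0.8; baseline-state correlation 0.5-0.9) |
|---|---|---|
| 0 | about 5% | about 5% |
| 0.2 | 36-70% | 13-32% |
| 0.4 | 92-100% | 35-89% |

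At r = 0.1 the rate is about 7-25% over both columns. Ranges within a cell reflect whether expectancy follows the observed score or the true state, and how well baseline HRSD predicts week-1 state.

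**3. If ED/WMH reaches expectancy only through early symptoms.** With linear growth its week-1 effect on HRSD is 2/8 = 0.25 points against an SD of √(25 + 16) = 6.4. At r = 0.4 that moves expectancy by only 0.4 × 0.25/6.4 = 0.016 SD, so path a is almost null. Simulated a×b, with a constant patient effect: 1-7% for linear growth; 4-13% if the effect is full by week 1 and r = 0.2; 23-65% if full and r = 0.4.

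**4. What a week-2 start does to a×b.** With a constant patient effect, nothing useful (30% to 31%, 43% to 47%, 65% to 65%). With drift and expectancy following the observed score, it helps (61% to 45%, 35% to 20%).

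**5. What adjustment costs when mediation is real.** Settings: a = −0.35, with 1.5 or 2.5 HRSD points per SD of expectancy.

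| When expectancy acts | Power, unadjusted to adjusted | Estimate |
|---|---|---|
| Fully by week 1 | 85% to 35%, or 99% to 67% | down about 61% |
| Half by week 1 | 81% to 76%, or 98% to 98% | down 26-31% |
| Only after week 1 | 75% to 97%, or 97% to 98% | no shrinkage |

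**The case against.** Week 1 is one row of eight, and removing it often changes little, so the time-order fault alone is close to a wording correction. That stands: the omitted early improvement matters more.

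The SAP already uses the earliest post-baseline expectancy, requires an overall ED/WMH effect before mediation is tested, and plans a sensitivity analysis for unmeasured confounding. That analysis does bear on mediator-outcome confounding. It does not address the concurrent row, and it is no substitute for adjusting for a variable collected at every visit.

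No document gives the tracking correlation. The Protocol's Specific Aims report little expectancy change in patients aged 60 or over in a preliminary study, but that compared assigned conditions and does not settle how expectancy follows symptoms within patients. If r is near zero there is no inflation.

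Week-1 HRSD may itself lie on the causal path. Open-group patients are told at assignment that they will receive active drug, so expectancy may act within the first week. This objection stands and limits the remedy.

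The reference to week-1 expectancy may be shorthand for the change already defined. That is possible, and one sentence would settle it.

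A reader might infer that path a is biased too. It is not: an ED/WMH effect on expectancy that runs through early improvement is part of the total path a effect.

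**Conclusion.** The point holds and should be fixed, with moderate confidence as to size. The text alone establishes that the week-1 outcome row is concurrent with the mediator and that measured improvement by week 1 is absent from path b. That this produces false mediation rests on an assumption the documents do not test: that week-1 expectancy follows early symptoms.

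The size is unknown. The low ends of the illustrative ranges apply when symptom state drifts between weeks and baseline HRSD predicts week-1 state well. The high ends apply when patient differences are stable and expectancy follows the true state. If ED/WMH affects expectancy only through early symptoms, a×b stays mostly near nominal unless tracking is strong and the ED/WMH effect is already full by week 1.

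Three stronger readings are not supported. The percentages are not error rates to expect in this trial. A significant a×b would not thereby be shown false; it would be open to a second explanation. Aim 1's randomised comparison is not affected.

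**What to change.** 1. Start the path b outcome at week 2.
2. Include baseline expectancy and baseline HRSD in both paths, so that the mediator is the stated change.
3. Co-report path b also adjusted for week-1 HRSD, leaving path a without it. Label it as a sensitivity analysis added after data collection, since the Protocol's status section says interventions are complete and only analysis continues.
4. If the indirect effect holds only without that adjustment, state that an expectancy effect and early improvement cannot be separated.
5. Report the planned unmeasured-confounder analysis beside both versions.

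The cost is SAP wording and one extra model on data already collected. Items 1 and 2 repair the time order and the mediator definition. The week-2 start lowers false positives only when symptom state drifts and expectancy follows the observed score. Item 3 leaves residual bias if expectancy follows the true state: with r of 0.2-0.4 and a constant patient effect, path b was still falsely significant in 28-99% of simulated trials. It also understates mediation if expectancy already acts by week 1. The adjusted model should therefore be neither the sole analysis nor a veto.

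### Aim 2 defines the mediator as early change in expectancy, but path b uses the week 1 level with no prespecified baseline expectancy term, so a*b can be significant when early change has no effect

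*SAP*

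**What the plan says.** The SAP, Analyses for Specific Aim 2, chooses the mediator so that it precedes the outcome: "we will use early change in expectancy (i.e., from baseline to week 1) as the primary measure for the mediator". The two mediation models are then written with the week 1 level.

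- Path a: "A model with week 1 expectancy as the outcome and ED/WMH as the primary predictor, controlling for baseline covariates". The covariates are not listed.
- Path b: "the same longitudinal mixed effect model described above with the addition of week 1 expectancy as a predictor will be used".

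The HRSD model that path b extends is Model 1, "only including predictors that do not involve randomized condition". Under Analyses for Specific Aim 1, the baseline term of Model 1 "is expectancy or HRSD at baseline", that is, the baseline value of whichever outcome is modelled. With HRSD as the outcome it is baseline HRSD. The covariate vector holds age, as the stratification variable, "and any baseline covariates exhibiting imbalance after randomization". Expectancy (CES items 2 and 4) and HRSD "will be collected at baseline and at weeks 1 through 8", so baseline expectancy is available.

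The indirect effect is the product of a and b, tested by bootstrap. Mediation is examined only once an overall effect of ED and/or WMH on HRSD has been shown. A sensitivity analysis for unmeasured confounders is planned.

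**The concern.** A week 1 level stands for early change only in a model that also holds the baseline level. Path b has no such term. Expectancy measured a week apart is likely to be correlated within patients. If baseline expectancy also predicts HRSD, the week 1 coefficient picks up that association even when the movement from baseline to week 1 does nothing.

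Hypothesis 2 says that ED and WMH act on outcome through a loss of expectancy effects. With path b as written, a significant a*b could instead reflect how hopeful patients were before treatment, and the analysis could not tell the two apart.

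**Working it through.** **No figure to reproduce.** The documents give no power, effect size or correlation for the mediation analysis. The check is a simulation in which week 1 expectancy has no effect on HRSD (true b = 0), so every significant a*b is false for the mediator as defined.

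**Inputs from the SAP.** n = 130 − 10 = 120, because the HRSD analysis drops the placebo patients, and two-sided α = 0.05 ("All tests will be two-sided"). Both are stated under Aim 1 and assumed to hold for Aim 2.

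**Assumed inputs, in SD units, not in the documents.** g: the ED–baseline expectancy correlation is −g. ρ: carry-over of expectancy from baseline to week 1. c: size of the effect of baseline expectancy on HRSD. a1: reduction in week 1 expectancy due to ED, given baseline.

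- E0 = −g·ED + √(1−g²)·noise
- E1 = ρ·E0 − a1·ED + √(1−ρ²)·noise
- HRSD (subject mean) = 0.5·H0 − c·E0 + 0.8·noise, where H0 is baseline HRSD

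**What path b estimates without E0.** Given ED, the variance of E1 is ρ²(1−g²) + (1−ρ²) = 1 − ρ²g², and its covariance with E0 is ρ(1−g²). Hence

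b = −c·ρ(1−g²)/(1−ρ²g²).

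For g = 0.3, ρ = 0.7, c = 0.4: b = −0.4 × 0.7 × 0.91/(1 − 0.49 × 0.09) = −0.4 × 0.637/0.9559 = −0.267. The true value is 0.

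**What path a estimates.** Without E0 it is −(gρ + a1); with E0 it is −a1. For g = 0.3, ρ = 0.7, a1 = 0 these are −0.21 and 0.

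**Bootstrap simulation** (600 trials per row, 400 resamples, percentile 95% interval for a*b). The last three columns give the percentage of trials with false mediation, by which path includes E0.

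| g | ρ | c | a1 | b, formula | b, simulated | neither | path a only | both |
|---|---|---|---|---|---|---|---|---|
| 0 | 0.5 | 0.4 | 0 | −0.200 | −0.201 | 4.0 | 3.5 | 0.2 |
| 0 | 0.7 | 0.4 | 0 | −0.280 | −0.276 | 4.5 | 4.5 | 0.2 |
| 0.3 | 0.5 | 0.4 | 0 | −0.186 | −0.186 | 22.3 | 2.3 | 0.2 |
| 0.3 | 0.7 | 0.4 | 0 | −0.267 | −0.266 | 55.2 | 5.3 | 0.2 |
| 0.5 | 0.7 | 0.4 | 0 | −0.239 | −0.246 | 81.8 | 5.0 | 0.3 |
| 0.3 | 0.7 | 0.2 | 0 | −0.133 | −0.129 | 23.7 | 1.8 | 0.5 |
| 0.3 | 0.7 | 0.4 | 0.25 | −0.267 | −0.263 | 89.5 | 84.5 | 4.5 |
| 0 | 0.7 | 0.4 | 0.25 | −0.280 | −0.276 | 71.5 | 89.0 | 6.2 |

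Path b is biased in every row. Whether that becomes false mediation depends on whether path a estimates something other than zero.

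**Other inputs.** Calling mediation when a and b are both significant, with g = 0.2 or 0.3, ρ = 0.5 or 0.7 and c = 0.2 or 0.4, false mediation was 5% to 58% with neither path adjusted (a1 = 0) and 18% to 88% with path a only (a1 = 0.25). A further run gave 6% to 54% and 20% to 83%, with at most about 5% when both paths were adjusted. These last figures are carried into the conclusion. In that run path b alone was falsely significant in 22% to 87% of trials without baseline expectancy and about 5% with it.

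**Requirement of an overall effect.** With neither path adjusted and no separate ED effect on HRSD, requiring a significant total effect cut false mediation from 6.5% to 0.4% at the mild end and from 52% to 15% at the severe end (51% to 17% in a second run). With an assumed separate ED effect of 0.25 SD, the severe end stayed at 52%.

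**Change score without baseline.** Using E1 − E0 with no baseline term gave 2% to 43% false mediation over the table's rows, with path b biased the other way (about +0.09 to +0.20).

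**The case against.** The strongest reply is that path a is meant to be adjusted. It controls for baseline covariates, and Model 1 carries baseline expectancy whenever expectancy is the outcome, so including it in path a is a natural reading. On that reading, patients with more ED/WMH merely starting with lower expectancy does not create false mediation: the rate is 1% to 5%. This stands, and it limits the concern. It does not repair path b, which then misleads if ED/WMH truly affects early change.

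Baseline expectancy could also enter path b as an imbalanced covariate. Imbalance between arms is a matter of chance, however, and has no bearing on whether baseline expectancy confounds week 1 expectancy and HRSD.

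The requirement of an overall ED/WMH effect is a real safeguard when ED/WMH has no other route to HRSD, and almost none when it has. The planned sensitivity analysis probes this kind of bias but does not remove it, and baseline expectancy is measured and can simply be adjusted for.

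The SAP overview speaks more broadly of mediation by decreased patient expectancy. On that wider view, a route through baseline expectancy could count as mediation. The SAP nevertheless names early change as primary; if the level is meant, the definition needs rewriting.

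Part of the SAP was not available, and the sections 3.3.B.5-6 that it cites are not shown. A covariate list may stand there.

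**Conclusion.** The point holds in a conditional form. The mediator is defined as change, path b is written with the level, and nothing in the available text prespecifies baseline expectancy in path b. The path b coefficient therefore mixes stable expectancy with early change.

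With true b = 0, n = 120 and the overall-effect requirement not yet applied, false mediation is about:

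- 6% to 54% if path a also omits baseline expectancy and ED/WMH is related to it;
- 20% to 83% if path a is adjusted and ED/WMH lowers early expectancy by an assumed 0.25 SD;
- no more than nominal if path a is adjusted and ED/WMH has no effect on early change;
- at most about 5% with both paths adjusted (6.2% in the worst bootstrap row of 600 trials).

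All of these rest on assumed correlations; stronger ones give higher rates. They show what can happen and do not estimate this trial's error rate.

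A reader might infer that lower baseline expectancy in ED/WMH patients is enough by itself to produce a false result, or that the trial's whole expectancy claim falls. The documents support neither. The first depends on a path a covariate list that the SAP leaves open. On the second, Aim 1 tests the expectancy hypothesis through the randomised contrast and does not use a*b.

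**What to change.** Name baseline CES expectancy (items 2 and 4) as a fixed covariate in both the path a and the path b models, whatever the balance between arms. The week 1 coefficient then estimates the effect of early change; week 1 level and change score give the same a and b once baseline is included. Replacing the level by a change score without the baseline term is not a substitute. If the pre-treatment level is meant to be part of the mechanism, redefine the mediator to say so.

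The cost is one degree of freedom per model, with the items entered as one score, and a line of SAP wording. No new data are needed. The protocol reports that interventions are complete and analysis is under way, so the change should be a dated clarification. If the mediation analysis has already been run, report it with and without the covariate.
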